recruitment of mental health experts, participant incentives, recording of interviews, and transcription and analysis of these interviews. Members of the ESTEEM lab's clinical team will conduct the interviews. Phase 3 will involve pilot testing the adapted cognitive-behavioral treatment through a randomized controlled trial with 60 SMW who report experiencing depression, anxiety, and alcohol abuse. The SMW will be randomized to either therapy or waitlist. Individuals assigned to therapy will receive 10 weekly individually-delivered sessions, directly after baseline assessment, that address minority stress mechanisms underlying SMW's depression, anxiety, and alcohol abuse. Individuals assigned to waitlist will be put on a waitlist for 3 months after baseline assessment, after which they will also receive the same treatment as the therapy group. While they are on waitlist, they are allowed to receive other treatment/therapy. There are no restrictions for participants on the waitlist. At their baseline appointment (and subsequently at their first therapy session) they will receive a list of community referrals containing sexual health and mental health resources. Participants on waitlist will not be re-assessed for eligibility once the 3 months have passed. At therapy, participants will be given questions to answer to track their progress (OASIS, ODSIS, and Heavy Drinking- these measures can be found in the therapy manual and measurements packet). At baseline, 3 months, and 6 months, participants will complete self-report surveys at home prior to coming in to their appointment. When participants are in the office, they will be given self-report assessments of mental and behavioral health outcomes and minority stress mechanisms, computerized behavioral tasks (Implicit Associations Task, Emotional Go No-Go Task, and Self-Referent Encoding Task), and a Time-Line Follow Back (TLFB) interview of past-90-day heavy alcohol use (all of which will be administered by trained research assistants). The TLFB will be recorded for quality assurance purposes and will only show the interviewers face and capture the participants voice. Incentives will be offered for each study visit: \$25 at baseline, \$25 at 3-month follow-up, \$75 at 6-month follow-up, and \$10 for each therapy session (therapy manual has been uploaded with this application). This study will entail the recruitment of 60 SMW participants through online recruitment methods, passive poster recruitment, and an existing list of SWMs who have expressed interest and consented to be contacted for any future research studies we conduct. All aspects of Phase 3 will take place at the Yale-sponsored ESTEEM lab in New York City under the supervision of [name]. Therapy sessions will be recorded and conducted by members of the ESTEEM lab's clinical team. Therapy sessions that are videotaped will only contain the therapists face, not the participants, but will catch the participants voice. These video recordings are for supervision and quality assurance purposes. Recordings of both therapy and the TLFB are not optional. Additionally, 15-20 participants enrolled in the study will be invited at random via e-mail to complete a follow-up qualitative phone interview about their experience in the study. These interviews will be audio recorded. Participants will be receive a \$40 Amazon gift card for completing a follow-up interview.

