☑ Through local NGO or other local contact	☐ Departmental/Center research boards	□ Newspape
☑ Table set-up / in-person recruitment of	☐ Snowball sampling	
public		
☐ Classroom recruitment	☑ Social Media (Twitter/Facebook):	

3. Targeted Enrollment: Give the number of participants:

a. Targeted for enrollment at Yale for this protocol

Phase 1: 20 sexual minority women **Phase 2:** 10 SMW experts **Phase 3:** 60 sexual minority women b. If this is a multi-site study, give the total number of participants targeted across all sites N/A

4. How was this estimate derived?

 \square Other:

For both Phase 1 and Phase 2, estimates were derived based on the number of interviews required to reach saturation in previous intervention development studies. For Phase 3, this part of the study is powered primarily to examine feasibility and acceptability. This phase will also allow us to determine the preliminary efficacy of the intervention. We will use Cohen's d and Hedge's g corrected for sample size, both of which express the average amount of individual change between intervention and control groups in terms of units of standard deviation. Group means on continuous variables typically begin to stabilize by 20-30 participants, and our waitlist design enables us to estimate effect sizes both by comparing intervention and control conditions at 3-months (n = 30/condition) and by examining pre-post effect sizes for the entire sample (n = 60). Our sample size provides sufficient power (1 - β =.8) to detect

intervention effects consistent with effect size estimates identified in our intervention research with sexual minority men in which the relative reduction in depression was 0.55 between intervention and control groups.

5. Process of Consent/Assent (NOTE: When a study includes minors, parent provide permission [not consent] for the child's participation, and the child provides assent for participation)

Describe the setting and conditions under which consent/assent will be obtained, including parental permission or surrogate permission and the steps taken to ensure participants' independent decision-making.

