In a first set of analyses, we used linear mixed models with maximum likelihood estimation and a compound symmetry covariance structure (selected based on fit criteria, i.e., lowest Akaike information criterion [AIC]) to test the Condition x Time interaction for all intervention outcomes including mental and behavioral health (e.g., depression), minority stress processes (e.g., rejection sensitivity), and universal risk processes (e.g., emotion regulation). To do so, we limited the data to baseline (time = 0) and 3 months postbaseline assessment (time = 1) and examined the Condition x Time interaction effect of receiving immediate EQuIP (condition = 1) versus receiving the 3-month waitlist (condition = 0). Thus, the estimate of interest compared preintervention to immediate postwaitlist outcomes in the immediate intervention group to prewaitlist and immediate postwaitlist outcomes in the waitlist control group. Effect sizes (d) for linear mixed models were calculated as mean pre–post change in the immediate intervention group to the mean pre–post change in the waitlist control group, divided by the pooled baseline standard deviation (Morris, 2008).

In a second set of analyses, we examined the clinical significance of observed changes in those mental health outcome measures that possess established clinical cutoffs (i.e., CES-D, ODSIS, OASIS). To do so, we used generalized linear mixed models with a logit link and binomial distribution to examine the Condition x Time interaction effect predicting the odds of meeting or

exceeding the clinical cutoff among participants receiving immediate EQuIP (condition = 1) versus those receiving the 3-month waitlist (condition = 0). For interpretability, we report proportions of participants meeting or exceeding clinical cutoff by condition and time.

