In a third set of analyses, we conducted a pooled analysis whereby data from all participants were pooled to examine change in outcome from immediate preintervention to postintervention using paired t tests (i.e., baseline to 3 months postbaseline for the immediate intervention group and 3-months postbaseline to 6-months postbaseline for the waitlist control group). Pooled analyses are useful in waitlist-controlled studies (where all participants ultimately receive treatment) to assess the pre–post effect of the intervention in a larger sample than the condition x time analyses allow. One participant assigned to the waitlist control group did not complete 3-month or 6-month assessments and was dropped from the pooled analysis (n = 59). Effect sizes (d) for pooled analyses were calculated as $\frac{2t}{\sqrt{df}}$.

Finally, we assessed the longer-term persistence of observed intervention effects by limiting analyses to immediate 3-months postbaseline (time = 1) and 6-months postbaseline (time = 2) among participants in the immediate intervention condition (condition = 1), the only participants to have completed assessments 3-months after receiving the intervention. Specifically, we examined the significance of changes between time points for all outcomes, including mental and behavioral health (e.g., depression), minority stress processes (e.g., rejection sensitivity), and universal processes (e.g., emotion regulation). Results were evaluated at p < .05.

References

Braun, V., & Clarke, V. (2006). Using thematic analysis in psychology. *Qualitative Research in Psychology*, *3*(2), 77-101.

Field, A. (2013). Discovering statistics using IBM SPSS statistics. SAGE.

George, D., & Mallery, P. (2010). SPSS for Windows step by step. A simple study guide and reference (10. Baskı). *GEN, Boston, MA: Pearson Education, Inc.*

Morris, S. B. (2008). Estimating effect sizes from pretest-posttest-control group designs. *Organizational Research Methods*, *11*(2), 364-386. https://doi.org/10.1177/1094428106291059

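### The pooled pre-post analysis turns a paired t into d with a two-independent-groups formula, on a different scale from the randomised d, and does not label its comparator-free result as uncontrolled

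*SAP*

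**What the plan says.** The SAP's Intervention Efficacy section describes four sets of analyses and does not rank them as primary or secondary. Two matter here.

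- **First set.** A linear mixed model on baseline and 3-month data tests Condition x Time for all outcomes. Here "the estimate of interest compared preintervention to immediate postwaitlist outcomes in the immediate intervention group" with the same period in the waitlist group. Its d compares the mean changes of the two arms and divides by the pooled baseline SD.
- **Third set.** Paired t tests on all participants pooled: months 0 to 3 for the immediate arm and months 3 to 6 for the waitlist arm. One waitlist participant without follow-up is dropped, leaving 59. The stated purpose is "to assess the pre–post effect of the intervention in a larger sample than the condition x time analyses allow". "Effect sizes (d) for pooled analyses were calculated as" 2t/√df.

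The protocol (Section V, item 4) announced in advance that pre-post effect sizes would be estimated in the whole sample of 60, next to the 3-month comparison of 30 per condition. It says that Phase 3 is powered mainly for feasibility and acceptability, with preliminary efficacy as a further aim. Under Research Plan, Phase 3, it says of the waitlist: "While they are on waitlist, they are allowed to receive other treatment/therapy" and "Participants on waitlist will not be re-assessed for eligibility once the 3 months have passed".

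**The concern.** There are two separate matters.

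The first is the formula. 2t/√df recovers a standardised difference from a t statistic that compares two independent groups of equal size. The third set has one group measured twice. Both sets then report a quantity under the symbol d, in different units, and the SAP does not say so. A reader who puts the pooled d beside the randomised d will see a larger value for reasons of scale alone. Effect sizes are the protocol's stated means of judging preliminary efficacy, so their scale matters.

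The second is interpretation. The paired test asks whether mean change differs from zero. Both pooled windows are treatment windows, and the one period without study treatment (waitlist, months 0 to 3) is left out. Recovery over time, regression to the mean after entry on elevated symptoms, and any other non-specific change therefore count as benefit. The SAP presents the result as an effect of the intervention, under an efficacy heading, without a caution.

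**Working it through.** **Inputs.** From the SAP, Intervention Efficacy: 60 randomised, 30 per arm; one waitlist participant dropped; d = 2t/√df; results judged at p < .05, sidedness not stated. Not given in either document: the pre-post correlation r, and any non-specific change. I assume equal SDs at all time points and show r from 0 to 0.8.

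**The plan's own figure.** 60 − 1 = 59 (30 immediate, 29 waitlist). This reproduces the SAP's n, and the paired df is 58.

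**What the formula returns.** For two independent groups of m each, t = (difference/SD) × √(m/2). So difference/SD = 2t/√(2m), which is close to 2t/√df. For paired data, t = (mean change/SD of change) × √n. So mean change/SD of change = t/√n. On a paired t, the SAP formula exceeds that quantity by

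2√(n/df) = 2√(59/58) = 2.017,

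whatever r is.

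**Against the first set's scale.** With equal SDs, SD of change = baseline SD × √(2(1 − r)). The printed d divided by the change in baseline SDs is therefore 2.017/√(2(1 − r)):

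| r | ratio |
|---|---|
| 0 | 1.43 |
| 0.3 | 1.70 |
| 0.5 | 2.02 |
| 0.7 | 2.60 |
| 0.8 | 3.19 |

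The square root cannot exceed 2, so under equal SDs the printed d is too large on this scale at every r. Only the amount depends on r.

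**Worked example.** Take a result just at two-sided p = .05, where t(0.975, 58) = 2.002.

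- Printed d = 2 × 2.002/√58 = 0.526, or 0.53.
- Mean change/SD of change = 2.002/√59 = 0.261.
- In baseline SDs: 0.261 × √(2(1 − r)) = 0.37 (r = 0), 0.26 (r = 0.5), 0.20 (r = 0.7), 0.16 (r = 0.8).

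If the test were one-sided, the printed value at the boundary would be 0.44.

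**The missing comparator.** If scores change by a in the immediate arm's window and b in the waitlist arm's window for reasons other than the intervention, the pooled mean moves by (30a + 29b)/59. The test cannot separate this from benefit. The following is illustration only, with assumed drifts in baseline SDs, zero intervention effect, a two-sided test and r = 0.5 to 0.7 (noncentral t, df = 58):

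- a = 0.2, b = 0: chance of p < .05 is 12% to 17%.
- a = 0.3, b = 0: 21% to 32%.
- a = 0.3, b = 0.1: pooled shift (9.0 + 2.9)/59 = 0.20, chance 33% to 50%.
- a = b = 0.2: pooled shift 0.20, also 33% to 50%.

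Any positive drift in the second window adds to the shift; it need not equal the first. Equal drift in both arms over months 0 to 3 cancels in the randomised change contrast, whose simulated rejection rate at 0.3 SD in each arm was 0.048 (r = 0.5) and 0.051 (r = 0.7).

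**The case against.** The strongest reply is that the pooled analysis is openly described and properly placed. The SAP states both windows, calls the result pre-post, sets it against the Condition x Time analyses and reports the dropped participant. The protocol announced such effect sizes beforehand, in a phase powered mainly for other aims. The randomised contrast comes first, covers every outcome and is untouched. The pooled test is more precise (SE 0.10 to 0.13 baseline SD, against 0.20 to 0.26 for the randomised change contrast, at r = 0.7 to 0.5), which is a fair reason to report it. All of this stands, and it makes the comparator limb a matter of labelling. It does not rescue the formula: announcing a pre-post effect size does not make an independent-groups conversion right for a paired test.

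Two stronger readings are tempting and are not supported.

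- A reader might infer that the pooled d is rigged to match the planning figure, because its smallest two-sided significant value, 0.53, lies near the 0.55 in "the relative reduction in depression was 0.55 between intervention and control groups". Any d computed from a test at fixed n has such a minimum. For the randomised change contrast it is about 2.002 × 0.260 = 0.52 at r = 0.5 and 2.002 × 0.202 = 0.40 at r = 0.7. The 0.55 is a between-group figure, and neither document compares it with the pooled d. The nearness follows from n.
- A reader might infer a known, large false-positive rate. The documents give no drift, so the percentages above follow wholly from assumed values. Because waitlisted participants are not re-screened at 3 months, 29 of the 59 begin their window without fresh selection on high scores, which weakens regression to the mean for about half of the data.

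**Conclusion.** The effect-size rule for the third set is wrong as written. It returns 2.02 times the mean change over the SD of change and, under equal SDs, 1.43 to 3.19 times the d that the first set's scale would give for the same change (r from 0 to 0.8, assumed). The direction does not depend on r; the size does.

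The lack of a comparator is real but is a smaller point. The SAP should not let a within-person change stand unlabelled as an effect of the intervention, but how much of that change is non-specific cannot be derived from the documents. Nor do they support the inference that the trial's efficacy analysis as a whole is compromised: the randomised baseline-to-3-month contrast is intact. What is missing is a statement that efficacy conclusions rest on it.

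**What to change.** In the SAP's third set:

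1. Replace 2t/√df with mean change divided by the pooled baseline SD, and give the estimate with a 95% CI.
2. Label the result *uncontrolled within-person change*. The new scale makes the units match; it does not make the estimate controlled.
3. State that efficacy conclusions rest on the randomised baseline-to-3-month Condition x Time contrast.
4. Show descriptively, each with a 95% CI, the immediate arm's 0 to 3 month change, the waitlist arm's 0 to 3 month change and the waitlist arm's 3 to 6 month change. The first two already enter the first set's d; only the third needs calculating.

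State the limits of the waitlist 0 to 3 month row: n = 29, other therapy allowed, and matched in calendar position only to the immediate arm's window. Its 95% CI half-width, t(0.975, 28) × √(2(1 − r)/29), is about 0.38 SD at r = 0.5 and 0.29 SD at r = 0.7. It is context, not a test.

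The cost is a few sentences and one small table from data already collected. The downside for the investigators is that the pooled d becomes smaller, by the ratios shown above, and that the more precise but uncontrolled test no longer serves as efficacy evidence.

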NCT03721276

Title of Research Project: Project EQuIP: Empowering Queer Identities in Psychotherapy

SAP Date 10.7.2019

Statistical Analysis Plan

Feasibility and Acceptability

Feasibility was assessed in terms of treatment attendance. Acceptability was assessed in terms of responses to the quantitative exit survey that all participants completed at 6-month follow-up and the qualitative exit interview conducted with 20 randomly selected participants after 6-month follow-up. Qualitative exit interviews were transcribed verbatim, and the third and eighth authors served as coders and double-coded all transcripts. Thematic analysis was used to identify patterns of responses, and emergent codes were categorized into larger themes (Braun & Clarke, 2006).

Intervention Efficacy

We assessed intervention efficacy using an intent-to-treat analysis including all eligible cases (n = 60). First, to determine randomization effectiveness, differences in baseline demographic characteristics were assessed between the immediate intervention (n = 30) and waitlist control (n = 30) conditions using t tests for continuous measures and chi-square tests for categorical measures. Income and gender identity differed between conditions (p < .05), with the waitlist control group reporting higher income and having a larger proportion of cisgender women; thus, we included income and gender identity as covariates in subsequent analyses.

Dependent variables were assessed for normality using skewness and kurtosis thresholds of ± 2 (Field, 2013; George & Mallery, 2010). Suicidality and internalized stigma were found to be non-normal; we therefore log-transformed these variables for further statistical tests (reassessment of skewness and kurtosis after transformation showed normal distribution).

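### The pooled pre-post effect sizes apply an independent-groups conversion to paired t tests, so each reported d is 2.02 times dz

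*SAP*

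**What the plan says.** In the third set of analyses under Intervention Efficacy, the SAP pools both arms to "examine change in outcome from immediate preintervention to postintervention using paired t tests". The immediate arm contributes its baseline to 3-month change. The waitlist arm contributes the change from "3-months postbaseline to 6-months postbaseline for the waitlist control group". One waitlist participant without follow-up assessments is dropped, leaving n = 59. The section then says "Effect sizes (d) for pooled analyses were calculated as" 2t/√df. It gives no source for the formula, no standardiser and no allowance for pairing.

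The first set of analyses also reports a quantity called d, but defines it differently: the difference between arms in mean pre-post change, "divided by the pooled baseline standard deviation".

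Protocol Section V, item 4 (derivation of the sample size) plans two effect-size estimates: one comparing conditions at 3 months, the other obtained "by examining pre-post effect sizes for the entire sample (n = 60"). It describes its effect sizes as being in standard-deviation units.

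**The concern.** The 2 in 2t/√df is there because the sample is split into two independent groups. A paired analysis has a single set of differences, so the 2 has no counterpart. The result is the mean change divided by about half the SD of change, which is neither dz nor a change in raw-score SD units.

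Phase 3 is a pilot whose efficacy aim is preliminary, so effect sizes are a main output. Two quantities carry the same symbol on different scales. A reader who compares them could credit the uncontrolled pooled change with a larger effect than the randomised comparison purely because of the formula. The Protocol also cites 0.55 as the between-group effect on depression in earlier work with sexual minority men. A pooled result that only just reaches p < .05 would be printed as 0.53 and would seem to match it.

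**Working it through.** **Inputs.** Paired t tests, d = 2t/√df and n = 59 come from the SAP's third set of analyses. The SAP's 60 randomised less the one dropped gives 59, which matches; paired df = 58. The documents give no pooled t or d, no pre-post correlation r and no ratio k of post SD to pre SD.

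**Where the formula belongs.** For two independent groups of m each, t = d × √(m/2) and df = 2m − 2. Then 2t/√df = d × √(m/(m − 1)). At m = 30 this is √(30/29) = 1.017 times d. A simulated 30 + 30 sample gave 0.468 against a pooled-SD d of 0.460, ratio 1.017.

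**What it gives for paired data.** Here t = dz × √n, so 2t/√df = 2 × √(n/(n − 1)) × dz. At n = 59 this is 2 × √(59/58) = 2.017 times dz. A simulated paired sample of 59 gave t = 5.780, dz = 0.752 and 2t/√df = 1.518, ratio 2.017. The factor depends only on n and rounds to 2.02 for any n from 41 to 67, so a few more missing pairs would not change it.

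| t (df = 58) | dz = t/√59 | Reported d = 2t/√58 |
|---|---|---|
| 2.00 | 0.26 | 0.53 |
| 3.00 | 0.39 | 0.79 |
| 4.00 | 0.52 | 1.05 |

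These t values are examples. The two-sided 5% critical value at 58 df is 2.002.

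**Against a raw-score SD.** With post SD = k × pre SD, the SD of change is pre SD × √(1 + k² − 2rk). The reported d is therefore 2.017/√(1 + k² − 2rk) times the mean change in pre-intervention SDs. With r and k as assumptions:

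| k | r = 0 | r = 0.3 | r = 0.5 | r = 0.7 |
|---|---|---|---|---|
| 0.8 | 1.58 | 1.87 | 2.20 | 2.80 |
| 1.0 | 1.43 | 1.70 | 2.02 | 2.60 |
| 1.5 | 1.12 | 1.32 | 1.52 | 1.88 |

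For example, a true change of 0.50 pre SD at r = 0.5 is reported as 0.50 × 2.017 = 1.01 when k = 1, or 0.50 × 1.52 = 0.76 when k = 1.5. Simulation of 20,000 trials with n = 59 gave mean reported values of 1.02 and 0.77.

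**When the factor falls to 1.** This requires 1 + k² − 2rk = 2.017² = 4.069, so k = r + √(r² + 3.069). The solutions are k = 1.75, 2.08, 2.32 and 2.59 at r = 0, 0.3, 0.5 and 0.7. For r ≥ 0, the post SD must be at least 1.75 times the pre SD before the formula stops inflating on this scale.

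**The case against.** The strongest counter-argument is about weight. The statistic is an uncontrolled pre-post summary. The randomised comparison has its own, properly defined d, the trial is powered mainly for feasibility and acceptability, and no test result changes. The SAP also prints both the formula and n, so a careful reader can recover dz by dividing by 2.02. All of that is true and limits the damage. It does not make the printed values right, and the Protocol names this estimate as one of two.

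A second objection is that 2.02 is exact only against dz, which the SAP never says it meant to report. On the scale a reader would probably assume, the factor is unknown. This stands. The table also uses the immediate pre-intervention SD, which mixes baseline scores with the waitlist arm's 3-month scores. Against the pooled baseline SD, each entry would be multiplied by baseline SD / pre-intervention SD, a ratio the documents do not give.

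Third, a corrected value need not be smaller on every scale. At k = 2 and r = 0 the factor is 2.017/√5 = 0.90. That is an extreme case, but only the reduction relative to dz is unconditional.

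Finally, no pooled t or d appears in the documents, so the error lies in the stated formula and its effect on particular results cannot be shown.

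**Conclusion.** The concern holds. The SAP applies the equal-size independent-groups conversion to paired t tests, and nothing elsewhere in the documents justifies or corrects it. Every pooled d based on 59 pairs is 2.02 times dz, whatever the outcome; this needs no assumption beyond n. On a raw-score scale the inflation is not a fixed number. Over the assumed ranges shown (r from 0 to 0.7, k from 0.8 to 1.5) it runs from 1.12 to 2.80.

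The error is confined to this one statistic. The paired t tests and their p values, the mixed models, the clinical-cutoff models and the Condition x Time d are unaffected. It should still be corrected before any pooled effect size is relied on, because it affects all of them.

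**What to change.** Delete 2t/√df and use one of two replacements:

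- **Mean pre-post change divided by a named SD, with a 95% confidence interval.** Use the pooled baseline SD if the scale is to match the Condition x Time d. If the immediate pre-intervention SD is used instead, say so and note that it combines scores from two time points. The SD must be on the analysed scale, which is the log scale for suicidality and internalized stigma.
- **t/√n, labelled dz**, with a statement that it is not on the scale of the Condition x Time d.

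In either case, state that the pooled value is an uncontrolled within-person change and not a difference in change between arms.

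The cost is one formula line and a recalculation from data already held. If dz is reported, the pooled values are about halved. On a raw-score scale the change depends on the observed SDs and correlation. No p value or model changes.
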